Study type/design	
This is an international, multicentre, randomised, open-label, prospective, controlled study. This study additionally includes a prospective observational arm for patients not eligible for randomisation who are treated in analogy to arm A of the randomised arm.

Primary objective	
Randomised arm To compare long-term pain response after dose-intensified image-guided hypofractionated SBRT employing SIB versus conventional radiation therapy for painful spinal metastases.
 
Prospective observational arm To assess the long-term level of pain after dose-intensified image-guided hypofractionated SBRT employing SIB

Hypothesis	
Randomised arm Dose escalation for painful spinal metastases using image-guided hypofractionated SBRT provides superior long-term pain response without adding toxicity as compared to conventional radiation therapy.
 
Prospective observational arm To prospectively evaluate safety and efficacy of SBRT for vertebral metastases; no formal statistical endpoint will be tested.

End-points	
Randomised arm Primary end-point:
 
 
• Pain response - improvement by <math>\geq 2</math> points on the pain Visual Analogue Scale at 6 months post-treatment at the treatment site.
 
 
Secondary end-points:
 
 
• Local metastasis control;
 
• Overall survival;
 
• Cancer-specific survival;
 
• Quality of life (QoL);
 
• Acute and late toxicity.
 
 
Prospective observational arm Primary end-point:
 
 
• Pain response - improvement by <math>\geq 2</math> points on the pain Visual Analogue Scale at 6 months post-treatment at the treatment site.
 
 
Secondary end-points:
 
 
• Local metastasis control;
 
• Overall survival;
 
• Cancer-specific survival;
 
• Quality of life (QoL);
 

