	
volume defined on CT/MR that is isotropically expanded with a 2 mm margin (the high-dose PTV) excluding the planning-at-risk volume (PRV) of the spinal cord and 2) the entire affected vertebra expanded isotropically with a 2 mm margin minus the high-dose PTV (the conventional-dose PTV or standard PTV, respectively). The spinal cord will be included into the conventional-dose PTV. In Arm A (investigational treatment) patients will receive image-guided static or rotational intensity-modulated radiation therapy with a prescription dose of 40 Gy and 20 Gy in 5 fractions to the high-dose PTV and conventional PTV, respectively, in the case of no epidural involvement; 48.5 Gy and 30 Gy in 10 fractions, if there is epidural involvement. There will be daily image-guided online correction of patient position errors.
 
In Arm B, patients will receive 3-dimensional conformal radiation therapy of the involved vertebrae using an institutional image-guidance protocol with a median prescription dose of 20 Gy in 5 fractions or 30 Gy in 10 fractions, depending on institutional protocol.
 
For arm A and arm B, the following procedures will be completed weekly during treatment:
 

• Physical and neurological examination;

• Weight, vital signs, Karnofsky performance status;

• Assessment of pre-specified protocol-specific adverse events;

• Recording of all other adverse events;

• Recording of pain and pain medications;

• Health-related QoL as measured by the EORTC QLQ-C15-PAL, EORTC-BM22 and EQ-5D-5L patient reported questionnaires (once at the last day of treatment).

 
There will be a prospective collection of planning CT and MR scans, treatment plans and all follow-up images of all patients enrolled into the study.
 
Prospective observational arm
 
Treatment phase
 
In the Prospective observational arm, patients will be treated exactly as patients in arm A of the randomised arm and they will undergo the same procedures.
 
Both arms
 
Post-treatment phase
 
For all patients, the following will be completed within 1 month <math>\pm</math>1 week (first follow-up visit):
 

• Physical and neurological examination;

• Weight, vital signs, Karnofsky performance status;

• Assessment of pre-specified protocol-specific adverse events;

• Recording of all other adverse events;

• Recording of pain and pain medications;

• Recording of concomitant medications;

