--	--

	
 
Health-related QoL as measured by the EORTC QLQ-C15-PAL, EORTC-BM22 and EQ-5D-5L patient reported questionnaires.
 
 
Both arms
 
Follow-up visits
 
Patients will be followed-up for 2 years after treatment completion or until death. Follow-up visits are scheduled at 3, 6, 12 and 24 months (<math>\pm 4</math> weeks) after treatment. The following procedures will be done at every follow-up visit:
 
 
Physical and neurological examination;
 
Weight, vital signs, Karnofsky performance status;
 
Assessment of pre-specified protocol-specific adverse events;
 
Recording of all other adverse events;
 
Recording of pain and pain medications;
 
Recording of concomitant medications;
 
Radiology as clinically indicated for osteolytic lesions, based on institutional protocol: CT and/or MR scans;
 
Health-related QoL as measured by the EORTC QLQ-C15-PAL, EORTC-BM22 and EQ-5D-5L patient reported questionnaires.
 

Study schedule	First quarter Q1 2016 (first patient enrolment) – Q4 2023 (last patient enrolment)
Sponsor-Investigator and Coordinating-Investigator	
[name] [name]          Department of Radiation Oncology          University Hospital Zurich          [name]          [name]          Switzerland          [contact]          [contact]          e-mail: [contact]

Study centres	Currently participating centres: 20 sites in Switzerland and in Europe

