Statistics	
Randomised arm
 
Sample size
 
160 participants will be recruited to the study. Based on prior research, a 40% pain response rate (<math>\geq 2</math> point improvement based on VAS) is expected in the standard treatment group and a 30% difference in pain response is expected between groups. At least 80 patients are needed in each treatment group to have 90% power of detecting this difference at the 5% level of significance in the presence of a 30% dropout rate.
 
Statistical analysis
 
Statistical analysis will be done in three populations: 1) Intent-to-Treat population (ITT) including all patients who were randomised and received at least one fraction of radiation therapy; 2) Per Protocol population (PP) including all patients of the ITT who have received study treatment according to randomisation without significant protocol violations and 3) safety-analysis set including all patients who were randomised and received at least one fraction of radiation therapy. To compare long-term pain control, Pearson's chi-square test with a continuity correction will be used on pain response rates across the two

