	
treatment arms. Wilson-method 95% confidence intervals will be provided for the pain response rate in each treatment group. The risk difference and its confidence interval will be provided as an effect measure, easily allowing for readers to calculate the 'number needed to treat'. Additionally, the odds ratio will be provided as a second effect measure. This measure allows for easy extension to logistic regression if other characteristics vary greatly across treatment groups. If daily oral morphine equivalent or epidural involvement vary greatly across treatment groups, a logistic regression model including treatment, daily oral morphine equivalent, epidural involvement, and centre will be used, which yields an odds ratio and its 95% confidence interval to summarize the difference in pain response between the treatment groups while controlling for other factors.
 
The Kaplan Meier estimator will be used for overall survival across the two treatment groups. (Semi-) Competing risk methods will be used to address the following events: local metastasis recurrence, cancer-specific death, and death by other causes. Cumulative incidence functions and sub-distribution hazards accounting for competing risks will be computed.
 
All safety analyses will be conducted on the safety-analysis set according to treatment received. For pre-specified protocol specific AEs, the point estimate of the difference between treatment arms, with 2-sided 95% CIs, will be provided. All other safety analyses will be presented in tabular format with the appropriate summary statistics for each treatment arm. QoL descriptive analysis will include the subset of the PP patients.
 
Prospective observational arm
 
Sample size
 
The sample size will not be pre-defined since no formal statistical hypothesis will be tested. For the University Hospital Zurich, we assume ca. 40 patients.
 
Statistical analysis
 
The statistical analysis will be mainly descriptive and exploratory. We report mean and standard deviation for continuous variables and median and interquartile range for ordinal variables and number and percentage for categorical variables. For the primary outcome, the proportion of patients with clinically relevant pain reduction will be estimated with Wilson 95% confidence intervals. Kaplan Meier curves will be plotted for overall survival. Competing risk methods will be used for local metastasis control, cancer-specific survival, and overall survival. Descriptive statistics will be used to describe quality of life outcomes and safety outcomes.
 
Interim Analysis
 
If the trial fails to recruit at least 50% of the initially planned patients in the randomised arms until 12/2020 (originally planned recruitment end), an interim safety and efficacy analysis of both randomised and prospective observational arms will be conducted.
 
If no safety concerns are raised after this interim analysis and there is a clinically relevant benefit of at least 10% for the experimental regimen

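### Quality of life in the randomised arm is planned only as a description of the per-protocol subset, with no commitment to a between-arm estimate and confidence interval

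*Protocol*

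**What the plan says.** The protocol synopsis lists QoL among the secondary end-points of the randomised arm (End-points). Under Study procedures, the screening list and the follow-up lists name the instruments: "Health-related QoL as measured by the EORTC QLQ-C15-PAL, EORTC-BM22 and EQ-5D-5L patient reported questionnaires". They are completed at screening, once on the last day of treatment, at the first post-treatment visit ("For all patients, the following will be completed within 1 month"), and then at the later visits: "Follow-up visits are scheduled at 3, 6, 12 and 24 months".

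Under Statistics, Randomised arm, one sentence covers the analysis of QoL: "QoL descriptive analysis will include the subset of the PP patients". The per-protocol (PP) population is defined in the same section as those ITT patients who "received study treatment according to randomisation without significant protocol violations".

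That section treats other end-points differently. Pain response gets a risk difference with a confidence interval, and an odds ratio. For pre-specified protocol-specific adverse events, "the point estimate of the difference between treatment arms, with 2-sided 95% CIs, will be provided".

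**The concern.** The sentence settles two things: the analysis is descriptive, and it is done in PP patients only. An SAP that follows the protocol inherits both, so this is more than detail left for later.

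Two consequences follow. First, nothing commits the trial to a QoL difference between arms with a measure of its precision. Summaries by arm alone do not tell a reader whether an observed difference is within chance. Second, PP membership depends on what happens after randomisation. The two arms receive different treatments in an open-label setting, so the patients who finish without significant violations may differ between arms. Even a simple side-by-side description in that set loses the protection of randomisation.

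At stake is a patient-reported secondary end-point of a palliative trial. It is collected repeatedly at some burden to patients, with a baseline score available to improve precision.

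**Working it through.** **Number of assessments** (Study procedures). Screening 1 + last day of treatment 1 + first post-treatment visit 1 + follow-up at 3, 6, 12 and 24 months 4 = 7. That is one baseline and six later measurements, each with three questionnaires.

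**What the Statistics section plans for the randomised arm**

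| End-point | Effect measure between arms | Confidence interval | Population |
|---|---|---|---|
| Pain response | risk difference, odds ratio | yes, for the risk difference | ITT and PP listed among the analysis populations |
| Protocol-specific adverse events | difference | yes, two-sided 95% | safety set, by treatment received |
| QoL | none named | none named | PP only |

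The adverse-event row shows that the plan already gives a difference with an interval, without a formal test, for an end-point on which the sample size is not based.

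**Number of patients available.** The protocol gives no sample size for QoL, so I start from its primary calculation: response 40% versus 70% (the 30% difference read as absolute), 90% power, two-sided 5%, no continuity correction. The mean proportion is 0.55.

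- n = [1.96 × √(2 × 0.55 × 0.45) + 1.2816 × √(0.40 × 0.60 + 0.70 × 0.30)]² / 0.30²
- n = (1.379 + 0.860)² / 0.09 ≈ 55.7, rounded up to 56 per arm
- With 30% dropout: 56 / 0.70 = 80 per arm, which is the protocol's figure.

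So 56 per arm is the number the protocol itself expects to be evaluable. Applying it to the 6-month questionnaires is an assumption.

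**Precision of a QoL difference.** The documents give no SD. Assume 20 to 30 points on a 0-100 scale.

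- Unadjusted 95% half-width = 1.96 × SD × √(2/n). With n = 56 this is 0.370 × SD: **7.4 points** (SD 20) to **11.1 points** (SD 30).
- Adjusted for the baseline score with correlation r, multiply by √(1 − r²). With assumed r = 0.5 the factor is 0.866: **6.4 to 9.6 points**.
- The equivalent gain in sample size is 1/(1 − r²) − 1: 33% for r = 0.5, and 19% to 56% for r = 0.4 to 0.6.

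**Sensitivity to the number analysed (unadjusted).** With all 80 per arm, 0.310 × SD: 6.2 to 9.3 points. With 45 per arm, an assumed PP count because the protocol gives none, 0.413 × SD: 8.3 to 12.4 points.

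**The case against.** A reader might infer that the trial will yield no between-arm QoL estimate at all. The text does not support this. A descriptive analysis can report a difference with an interval, and the protocol does not forbid it. The accurate statement is that it does not commit to one.

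A reader might also assume that the plan is to tabulate unadjusted means by visit and ignore baseline. The protocol does not say so. Means and standard deviations are mentioned only for the observational arm. The precision gain above therefore shows what baseline adjustment offers over an unadjusted difference. It is not a loss shown to follow from the plan.

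The following can also be said for the plan:

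- **SAP content.** Scale, model and missing-data handling are commonly left to an SAP, which is not shown here. This stands, and the fix leaves the model open. It does not cover the word descriptive or the PP restriction, which the protocol itself fixes.
- **No formal test is needed.** The sample is sized for pain response only, and describing a secondary end-point is legitimate. This stands. An estimate with its interval is not a test, and the plan already uses one for adverse events.
- **QoL is not part of the stated goal.** The synopsis rationale describes palliation as pain relief, vertebral stability and neurological function. It is therefore fair not to treat QoL as the deciding end-point. It is still a listed secondary end-point.
- **Multiplicity.** Three questionnaires at six later visits give at least 3 × 6 = 18 differences, more if several scales are used. This is a good reason to name one time point.
- **Death and dropout.** A repeated-measures model would not cure changing membership over visits. It relies on a missing-at-random assumption and does not resolve death before a visit. Nor does the protocol say when the 30% dropout occurs, so the amount of early data such a model could recover is unknown. All of this stands and limits what the fix can promise.

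**Conclusion.** The concern holds in a limited form. For a secondary end-point with a baseline and six later measurements, the protocol fixes a descriptive analysis in a set selected after randomisation, and names no between-arm estimate with a confidence interval. That is out of line with its own treatment of pain response and protocol-specific adverse events. If a difference were reported under the present sentence, it would come from PP patients and would not be a comparison as randomised.

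The size of any bias from the PP restriction cannot be calculated, because the protocol gives no expected rate of violations by arm. What can be shown is that a useful estimate is feasible: a 95% half-width of about 7.4 to 11.1 points unadjusted, or 6.4 to 9.6 with baseline adjustment. These figures rest on an assumed SD of 20 to 30, an assumed correlation of 0.5, and 56 patients per arm with a 6-month score. This is a worthwhile correction to a secondary analysis. It does not affect the primary comparison.

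**What to change.** Replace the QoL sentence under Statistics, Randomised arm, with:

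> For QoL, the between-arm difference at 6 months, adjusted for baseline score, is given with its 95% CI in the ITT population as randomised; other visits are summarised by arm with the numbers alive and completing the questionnaire; the PP analysis is supportive.

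Six months matches the time point of the primary end-point. The exact model may be left to the SAP. If a repeated-measures model is chosen, state its missing-at-random assumption and that it does not resolve death before the visit. The protocol's ITT population requires at least one fraction of radiotherapy, so here as randomised means that those patients are analysed by assigned arm.

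The cost is a little more analysis on data already being collected. The downside is additional secondary estimates, which should be labelled as not controlled for multiplicity.

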--	---

Dose-intensified Image-guided Fractionated Stereotactic Body Radiation Therapy for Painful Spinal Metastases versus Conventional Radiation Therapy: a Randomised Controlled Trial (DOSIS RCT)

	regarding the primary endpoint, the recruitment will be continued. Otherwise, the study will be terminated due to slow accrual and futility.
GCP statement	This study will be conducted in compliance with the protocol, the current version of the Declaration of Helsinki, the ICH-GCP or ISO EN 14155 (as far as applicable) as well as all national legal and regulatory requirements.

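### The interim rule requires a futility stop below a 10% benefit with no minimum number of 6-month results, and the stated 90% power does not allow for it

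*Protocol*

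**What the plan says.** The rule is in the Statistics row of the Synopsis, under Interim Analysis. The trigger is recruitment: "If the trial fails to recruit at least 50% of the initially planned patients in the randomised arms until 12/2020". If it is met, "an interim safety and efficacy analysis of both randomised and prospective observational arms will be conducted". Recruitment goes on only if no safety concern arises and "there is a clinically relevant benefit of at least 10% for the experimental regimen" on the primary endpoint, which is pain response 6 months after treatment. The alternative is not discretionary: "Otherwise, the study will be terminated due to slow accrual and futility".

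The text gives no minimum number of patients or of 6-month assessments. It does not say whether 10% is absolute or relative, or whether it applies to a point estimate or a confidence bound.

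The sample-size text in the same row expects 40% response in the control group, and "a 30% difference in pain response is expected between groups". It then states: "At least 80 patients are needed in each treatment group to have 90% power of detecting this difference". The test level given is 5%, and the figure allows for 30% of patients dropping out. The interim rule is not mentioned there.

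**The concern.** The trigger itself guarantees that the look takes place with little data, and the slower the accrual, the less data there are. A fixed 10% cut-off then becomes noisier exactly when the decision matters most. Three things are at stake.

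- A treatment with the full planned effect can be abandoned by chance.
- The stated power does not describe the design once a mandatory stop can occur.
- A result that leaves the trial more likely than not to succeed on its own assumptions would be reported as futility, and readers could take it as evidence against SBRT.

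The contingency was not remote. Version 4.0 is dated 11/12/2020, within weeks of the trigger date, and the Synopsis runs enrolment on to Q4 2023.

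**Working it through.** **Inputs.** From the Synopsis: response 40% versus 70%, 5% level (taken as two-sided), 90% power, 30% dropout, 80 per arm, 1:1 allocation, trigger below 50% of 160, threshold 10%. Assumed: 10% is an observed absolute difference, and 39, 27, 20 or 10 patients per arm are evaluable at the look. The protocol does not give that number.

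**1. The plan's own figure.** With the mean rate 0.55,

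n = [1.960·√(2·0.55·0.45) + 1.282·√(0.7·0.3 + 0.4·0.6)]² / 0.30² = (1.379 + 0.860)² / 0.09 = 55.7, so 56 evaluable per arm.

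56 / 0.70 = 80 per arm. The stated size is reproduced, using the test without continuity correction.

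**2. Patients at the look.** Fewer than 0.5 × 160 = 80 randomised is about 39 per arm. 39 × 0.70 = 27 evaluable per arm. If the look is taken promptly at 12/2020, recent patients lack 6-month data and the number is lower.

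**3. Chance of stopping and power.** With m evaluable per arm, A ~ Bin(m, 0.70) and B ~ Bin(m, 0.40), the trial stops if (A − B)/m < 0.10. Power with the rule is the exact joint probability of passing the look and rejecting in favour of SBRT at 56 per arm, with the interim patients included. Without the rule, exact power is 89.6% for the uncorrected chi-square test and 85.7% for the planned continuity-corrected test.

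| Evaluable per arm | P(stop) at 70% vs 40% | Power with rule, uncorrected | Power with rule, corrected |
|---|---|---|---|
| 39 | 2.7% | 89.2% (−0.3) | 85.5% (−0.2) |
| 27 | 5.6% | 87.2% (−2.4) | 83.9% (−1.8) |
| 20 | 6.9% | 85.8% (−3.8) | 82.6% (−3.1) |
| 10 | 12.0% | 80.9% (−8.7) | 77.9% (−7.8) |

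Losses are in percentage points, from unrounded values. The risk is not smooth in m because counts are whole numbers. At 12 per arm a lead of two responders is needed to pass, and P(stop) is 18%. At 10 per arm a lead of one is enough.

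If 10% is read as a relative benefit, P(stop) is 1.2%, 3.1%, 5.3% and 12.0% at 39, 27, 20 and 10 per arm.

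**4. Is 10% futile?** Let t = m/56 and let the variance per patient pair be 0.21 + 0.24 = 0.45. The design drift is θ = 0.30/√(0.45/56) = 3.347. For an observed difference d, B(t) = √t · d/√(0.45/m), and

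CP = 1 − Φ{[1.960 − B(t) − θ(1 − t)] / √(1 − t)}.

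At d = 0.10:
- m = 27: t = 0.482, B = 0.538; (1.960 − 0.538 − 1.733)/0.720 = −0.43, CP = 67%.
- m = 20: t = 0.357, B = 0.398; (1.960 − 0.398 − 2.151)/0.802 = −0.74, CP = 77%.
- m = 10: t = 0.179, B = 0.199; (1.960 − 0.199 − 2.749)/0.906 = −1.09, CP = 86%.

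An observed 10% itself passes. The best results that would still stop the trial are 2/27 = 7.4%, 1/20 = 5% and 0/10 = 0%. The same formula gives them CP of 59%, 69% and 81%.

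At the extreme of 39 evaluable per arm (t = 0.696, B = 0.777; (1.960 − 0.777 − 1.016)/0.551 = 0.30), CP at 10% is 38%. The mislabelling therefore concerns looks with about 27 or fewer per arm.

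**The case against.** **The loss is modest and conditional.** It arises only if the look is triggered, and near the cap it is 0.3 to 2.4 points with the uncorrected test. The larger figures need few evaluable patients: 10 per arm after 30% dropout means about 29 randomised in total (20/0.70), after enrolment planned from Q1 2016. This stands, and it limits the size of the point.

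**The rule does useful work.** With no true difference at 40%, it stops the trial 59% to 79% of the time over 10 to 39 per arm. How to weigh a wrong stop against a wrong continuation is a choice for the sponsor, especially in a trial below half its target. This also stands. A conventional conditional-power cut-off is therefore not an obvious improvement: a 20% cut-off at 20 per arm would stop a null trial only about 7% of the time, against 69% now.

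**Details may be in the SAP.** The estimator and data cut-off may well be there. But the protocol itself fixes a mandatory consequence, a threshold and a power figure, and these do not fit together.

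**Stronger readings that the documents do not support.**
- A reader might set the corrected-test results of roughly 78% to 84% at 10 to 27 per arm against the stated 90% and blame the rule. Most of the gap at 27 per arm is the continuity correction, which gives 85.7% with no interim at all.
- A reader might infer that observational patients, some of them pain-free, enter the decision. A benefit for the experimental regimen needs a control, and only the randomised part has one.
- A reader might object that continuing reveals a benefit of at least 10%. Any published continue-or-stop rule reveals that its threshold was passed.
- A reader might suspect inflation of type I error. The rule allows no early claim of efficacy, so there is none.

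**Conclusion.** The point holds in limited form. The protocol fixes a binding futility stop at a 10% benefit without a minimum amount of 6-month data, and states a power that ignores it. With about 27 evaluable per arm, the most that the plan's own dropout allows, a trial with the planned effect stops 5.6% of the time and conditional power at the threshold is 67%. The damage becomes serious only at small numbers: a 12% to 18% risk of a wrong stop at 10 to 12 per arm, and 8.7 points of power at 10 per arm with the uncorrected test. Nothing in the protocol's text prevents a look at such numbers.

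These figures assume that the look is triggered, that 10% is an observed absolute difference, that the true rates are 70% and 40%, that no safety stop occurs, and that a continuing trial reaches 56 evaluable per arm. The number evaluable at the look is an assumption throughout.

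**What to change.** Amend the Interim Analysis paragraph to:

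1. State that the 10% is an absolute difference in 6-month response between the two randomised arms.
2. Apply the rule only once a stated minimum has 6-month VAS results: at least 20 per arm, preferably about 27.
3. Make the efficacy part non-binding, and report a stop for slow accrual separately from one for futility.
4. Restate the power with the rule included. By the table above, with the look at 20 or 27 per arm, this is 85.8% or 87.2% for the uncorrected test and 82.6% or 83.9% for the planned corrected test.

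The cost is one paragraph and a short calculation. The interim may have to wait some months for 6-month data, and the stated power becomes slightly lower.
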